### 9.5. SERIOUS ADVERSE EVENTS REPORTING

The reporting of SAEs by the Sponsor to Regulatory Authorities (e.g., FDA) is a regulatory requirement.

All SAEs must be reported immediately (within 24 hours of learning of the event) via entry into the EDC system with at least the event term, start date, and IP relationship. In the event EDC entry is unavailable, notification must occur via email or phone to the contact below:

[name] Cassava Sciences, Inc.

Email: [contact]

[contact]

Do not delay reporting a suspected SAE to obtain additional information. Any additional information, if collected, can be reported to the Sponsor as a follow-up to the initial report.

If a partial SAE report was initially provided then a completed SAE report must be entered into the EDC within five (5) working days. The Investigator is responsible for reporting SAEs to the IRB according to IRB guidelines. The Sponsor will report SAEs to FDA as required.

In the case of a death or other SAE that has occurred within 30 days after receiving study drug, the Principal Investigator must also report such an event within 24 hours of being notified.

In the event of any SAE (other than death), the subject will be instructed to contact the study physician (Principal Investigator or designee) using the phone number provided in the ICF. All subjects experiencing an SAE will be seen by a Principal Investigator or designee as soon as feasible following the report of an SAE.

### 10. STATISTICAL CONSIDERATIONS

### 10.1. ANALYSIS POPULATIONS

All subjects who receive study medication will be included in safety analyses.

### 10.2. SAFETY ANALYSIS

Adverse events reported on case report forms will be mapped to preferred terms and organ systems using the MedDRA mapping system. Vital signs and clinical laboratory results will be descriptively summarized in terms of change from screening values.

### 10.3. SAMPLE SIZE

Up to 180 subjects may be enrolled in this study. Eligible subjects include those who completed PTI-125-04.

### 11. STUDY TERMINATION

The study will be terminated following FDA approval of simufilam or program termination or at any time at the discretion of the Sponsor.

### 12. DATA COLLECTION, RETENTION AND MONITORING

### 12.1. CASE REPORT FORMS

Electronic case report forms (eCRFs) will be used for each subject. The subjects in the study will not be identified by name on any study documents to be collected by the Sponsor (or CRO designee) but will be identified by a unique subject number.

All clinical information requested in this protocol will be recorded in the eCRFs provided by CSI. In case of error, the correction will be noted, initialed, and dated.

eCRFs must be reviewed and verified for accuracy by the Principal Investigator and signed-off before collection by the Sponsor (or CRO designee). Paper source documents, if used, will remain at the Investigator's site after study completion.

### 12.2. AVAILABILITY AND RETENTION OF INVESTIGATIONAL RECORDS

The Investigator must make study data accessible to the monitor, other authorized representatives of the Sponsor (or designee) and Regulatory Agency (e.g., FDA) inspectors upon request. To assure accuracy of data collected in the eCRFs, it is mandatory that Sponsor representatives have access to original source documents (e.g., subject records, subject charts, and laboratory reports). During review of these documents, the subject's anonymity will be maintained with adherence to professional standards of confidentiality and applicable laws. A file for each subject must be maintained that includes the signed ICF and all source documentation related to that subject. The Investigator must ensure the reliability and availability of source documents for the eCRF.

Investigators are required to maintain all study documentation until notification by CSI that any records may be discarded.

The Investigator is responsible for maintaining adequate case histories in each subject's source records.

### 12.3. SUBJECT CONFIDENTIALITY

All reports and subject samples will be identified only by the assigned subject number and initials, as applicable by local law, to maintain subject confidentiality. Additional subject confidentiality measures (as required by region) will be covered within the Clinical Trial Agreement for each site as applicable.

### 12.4. LIABILITY

In the event of a side effect or injury, appropriate medical care as determined by the Investigator, or his/her designated alternate will be provided.

If a bodily injury is sustained resulting directly from the study drug, the Sponsor will reimburse for reasonable physician fees and medical expenses necessary for treatment of only the bodily injury which is not covered by the subject's medical or hospital insurance, provided that the injury is not due to a negligent or wrongful act or omission by the study doctor and his/her staff. No other compensation of any type will be provided by the Sponsor. Compensation for lost wages, disability, or discomfort due to the study is not available.

### 12.5. ETHICAL AND LEGAL ISSUES

The Investigator and site personnel are responsible for conducting this study in accordance with the ICH, GCP, and all other applicable laws and regulations.

### 12.5.1. Institutional Review Board

The protocol and Informed Consent Form must be approved by an IRB before the study is initiated. The IRB must comply with U.S. CFR 21 Part 56 and local laws.

Documentation of IRB approval must be provided to the Sponsor. Investigators are responsible for the following:

- Obtaining IRB approval of the protocol, Informed Consent Form, and any
  advertisements to recruit subjects and IRB approval of any protocol amendments
  and Informed Consent Form revisions before implementing the changes.
- Providing the IRB with any required information before or during the study.
- Submitting progress reports to the IRB, as required, requesting additional review and approval, as needed; and providing copies of all relevant IRB communications to the Sponsor.
- Notifying the IRB within 15 calendar days of all SAEs and unexpected AEs related to study drug reported by the Sponsor to the Investigator.

### 12.6. INFORMED CONSENT FORM

The Sponsor (or designee) must review the Investigator's proposed ICF prior to IRB submission for approval. An IRB-approved copy of the Informed Consent Form is forwarded to the Sponsor.

The ICF documents study-specific information the Investigator provides to the subject and the subject's agreement to participate. The Investigator explains in plain terms the nature of the study along with the aims, methods, anticipated benefits, potential risks, and any discomfort that participation may entail. The ICF must be signed and dated before the subject enters the study. The original ICF and any amended ICF, signed and dated, must be retained in the subject's file at the study site and a copy must be given to the subject.

### 13. INVESTIGATOR RESPONSIBILITIES

The Investigator agrees to:

• Conduct the study in accordance with the protocol, except to protect the safety,

[figure not shown]
rights, or welfare of subjects.

[figure not shown]
- Personally conduct or supervise the study.
- Ensure that requirements for obtaining informed consent and IRB review and approval comply with ICH, CFR 21 Parts 50 and 56, and local laws.
- Report to the Sponsor any AEs that occur during the study in accordance with ICH, CFR 21 Part 312.64, and local laws.
- Read and understand the Investigator's Brochure including potential risks and side effects of the drug.
- Ensure that all associates, colleagues, and employees assisting in the conduct of the study are informed about their obligations in meeting the above commitments.
- Maintain adequate records in accordance with ICH, 21 CFR Part 312.62, and local laws and have records available for inspection by the Sponsor, FDA, or other authorized agency.
- Promptly report to the IRB and the Sponsor all changes in research activity and unanticipated problems involving risks to subjects or others (including amendments and expedited safety reports).
- Comply with all other requirements regarding obligations of Clinical Investigators and all other pertinent requirements listed in ICH, 21 CFR Part 312, and local laws.

# 15. APPENDIX A – STUDY DESIGN SCHEMATIC

# 16. APPENDIX B - SCHEDULE OF EVENTS FOR ACTIVE PARTICIPANTS

STUDY PROCEDURE	Study Day 1 a	Week 12	Week 24	Week 36	Week 48	Week 60	Week 72	Week 84	Week 96	Repeat Visit A e	Repeat Visit B f	End of Study / Early Term
Informed Consent	X											
Vital Signs	$^{ m q}{ m X}$	X	X	X	X	X	X	X	X	X	X	X
Height & Weight	${}_{q}X$	X	X	X	X	X	X	X	X	X	X	X
Physical Examination	2 q X	*	*	*	Χc	*	*	*	ο X	*	$X^{\mathfrak{c}}$	Χc
Chemistry, Hematology, Urinalysis	q X		X		X		X		X		X	X
ECG	${}_{q}X$		X		X		X		X		X	X
Drug Dispensation d	X	X	X	X	X	X	X	X	X	X	X	
Drug Accountability		X	X	X	X	X	X	X	X	X	X	X
Adverse Events	$X^{b}$	X	X	X	X	X	X	X	X	X	X	X
Concomitant Medications	${}^{q}X$	X	X	X	X	X	X	X	X	X	X	X
C-SSRS – Since Last Visit	$^{ m q}$ X	X	X	X	X	X	X	X	X	X	X	X

\* Brief physical exam.

<sup>a Study Day 1 will take place during the Month 24 Visit for study PTI-125-04.

<sup>b Data collected at Month 24 Visit for study PTI-125-04 will be used.

<sup>c Full physical examination at Day 1 (as part of Month 24 Visit from study PTI-125-04), Week 48, Week 96, and Repeat Visit B, and at End of Study or Early Term Visit.

<sup>d Drug will be dispensed at Study Day 1 and every 12 weeks.

<sup>e Repeat Visit A occurs 12 weeks following the Week 96 visit and then reoccurs every 24 weeks thereafter. f Repeat Visit B occurs 12 weeks following the first Repeat Visit A and then reoccurs every 24 weeks thereafter.

# 17. APPENDIX C - SCHEDULE OF EVENTS FOR RE-ENTRY PARTICIPANTS

STUDY PROCEDURE	Re-entry Day 1	Re-entry Week 4 º	Repeat Visit A c	Repeat Visit B d	End of Study / Early Term
Informed Consent	X				
Medical History	X				
Inclusion/Exclusion Criteria	×				
Vital Signs	X	X	X	X	X
Height & Weight	X	X	X	X	X
Physical Examination	X a	*	*	$X^{a}$	$X^{a}$
Chemistry, Hematology, Urinalysis	X	X		X	X
ECG	X	X		X	X
Drug Dispensation b	X		X	X	
Drug Accountability		X	X	X	X
Adverse Events	X	X	X	X	X
Concomitant Medications	X	X	X	X	X
C-SSRS – Since Last Visit	X	X	X	×	X

\* Brief physical exam.

<sup>a Full physical examination at Re-entry Day 1, Repeat Visit B, and at End of Study or Early Term Visit.

<sup>b Drug will be dispensed at Re-entry Day 1 and every 12 weeks thereafter.

<sup>c Repeat Visit A occurs 12 weeks following the Re-entry Day 1 visit and then reoccurs every 24 weeks thereafter.

<sup>dRepeat Visit B occurs 12 weeks following the first Repeat Visit A and then reoccurs every 24 weeks thereafter.
e Re-entry Week 4 visit only for subjects who completed the PTI-125-09 study >60 days prior to completing Re-entry Day 1.

## **LIST OF FIGURES**

## Figure 1 - Study Design Schematic

#### 1. LIST OF ABBREVIATIONS AND DEFINITION OF TERMS

Only abbreviations and terms relevant to the SAP are repeated herein. The reader is referred to the protocol for the complete and comprehensive list of abbreviations and definitions of terms for the study.

AD	Alzheimer's Disease
AE	Adverse Event
B.I.D	Twice a day/twice daily
CRF	Clinical Report Form
CSR	Clinical Study Report
C-SSRS	Columbia Suicide Severity Rating Scale
DSUR	Development Safety Update Report
ECG	Electrocardiogram
eCRF	Electronic Case Report Form
FDA	Food and Drug Administration
MedDRA	Medical Dictionary for Regulatory Activities
MMSE	Min-Mental Status Exam

Live v1.0
10 Ech 2025

NTF	Note to File
OLE	Open Label Extension
PT	Preferred Term
SAE	Serious Adverse Event
SAE	Serious Adverse Event
SAP	Statistical Analysis Plan
SAS	Statistical Analysis System
SOC	System Organ Class
TEAE	Treatment Emergent Adverse Event

#### 2. INTRODUCTION

#### 2.1. **Preface**

This document presents an abbreviated statistical analysis plan (SAP) for Cassava Sciences' open-label extension (OLE) Protocol PTI-125-09 for the Treatment of Alzheimer's Disease. An abbreviated SAP is being prepared as the study and the program are being closed. A full Clinical Study Report (CSR) is not expected to be prepared, but safety data will be provided to allow for inclusion in the Development Safety Update Report (DSUR) later in 2025.

Reference materials for this statistical plan includes Protocol PTI-125-09. The latest version of this protocol is Amendment #3, Dated: September 18, 2024. Amendment #3 allowed for the OLE study to be extended through FDA approval of simufilam or program termination. The program was terminated shortly after approval of this amended protocol by the Central IRB.

The abbreviated statistical analysis plan (SAP) described hereafter is an a priori plan. The abbreviated SAP will be finalized and approved prior to database lock.

#### 2.2. **Purpose of Analyses**

The purpose of this abbreviated Statistical Analysis Plan (SAP) is to provide a description of the statistical methods used to present safety results consistent with protocol PTI-125-09: "An Open-Label Extension of the PTI-125-04 Study Evaluating the Safety and Long-Term Treatment of Simufilam in Mild-to-

## **Statistical Analysis Plan**

Moderate Alzheimer's Disease Patients." Simufilam is an investigational drug candidate under development by the protocol Sponsor, Cassava Sciences, Inc.

Results from these analyses may be used in the DSUR planned for submission in 2025.

Post-hoc exploratory analyses not identified in this SAP are not expected, but may be performed to further examine the study data. These analyses will be clearly identified, where appropriate, in the final clinical study report. Additional analyses not prospectively identified in this SAP may also be completed for publications, or regulatory or funding inquiries. These analyses, if performed, may not be reported in the clinical study report, but will be fully documented in the document containing the additional analyses.

This SAP includes details of data handling procedures and statistical methodology. The final statistical analysis will proceed in accordance with this SAP as approved by Cassava Sciences, Inc., and Axiom Real-Time Metrics. Any material deviation from this SAP will be documented in a Note to File (NTF). Any material deviations from methods described in the protocol are also detailed and explained in this SAP.

This version of the SAP will be finalized and approved by the Sponsor and Axiom prior to database lock. Statistical programming of study data will be initiated as study data accumulates to ensure analysis program are setup and readily available prior to statistical delivery.

## 2.3. Summary of Statistical Analysis Changes to the Protocol

The analyses described in this analysis plan have been modified from the analyses described in the study protocol.

#### 3. STUDY ENDPOINTS

## 3.1. Primary Endpoint

The overall study objective is to assess the long-term safety and tolerability of simufilam.

Descriptive summary of vital signs, clinical laboratory parameters, and ECG results during the treatment period will not be performed, as identified in the protocol. Significant results of these assessments, as assessed by the Investigators, will be captured as treatment emergent AEs and SAEs and summarized in basic safety tabulations and provided in data listings.

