### 9. ADVERSE EVENTS/SERIOUS ADVERSE EVENTS

### 9.1. ADVERSE EVENTS - DEFINITION

An adverse event (AE) is any undesirable event that occurs to a subject during a study, whether or not that event is considered study drug-related. Monitoring for AEs will start at dosing. Examples include:

- Any treatment-emergent signs and symptoms (events that are marked by a change from the subject's baseline/entry status [e.g., an increase in severity or frequency of pre-existing abnormality or disorder])
- All reactions from study drug, an overdose, abuse of drug, withdrawal phenomena, sensitivity, or toxicity to study drug
- Apparently unrelated illnesses
- Injury or accidents (Note: if a medical condition is known to have caused the injury or accident, the medical condition and the accident should be reported as two separate medical events [e.g., for a fall secondary to dizziness, both "dizziness" and "fall" should be recorded separately])
- Extensions or exacerbations of symptoms, subjective subject-reported events, new clinically significant abnormalities in clinical laboratory, physiological testing, or physical examination

All AEs, whether or not related to the study drug, must be fully and completely documented on the AE page of the eCRF and in the subject's clinical chart.

In the event that a subject is withdrawn from the study because of an AE, it must be recorded on the eCRF as such. The subject should be followed and treated by the Investigator until the abnormal parameter or symptom has resolved or stabilized.

The Investigator must report all directly observed AEs and all spontaneously reported AEs. The Investigator will ask the subject a non-specific question (e.g., "Have you noticed anything different since your dose of the study medication?") to assess whether any AEs have been experienced since the last assessment. AEs will be identified and documented on the eCRF in appropriate medical terminology. The severity and the relationship to the study drug will be determined and reported on the eCRF (see below).

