## 8.2. Clinical Laboratory Evaluations

Listings of individual laboratory parameters by visit will not be presented. Significant laboratory results, as assessed by the Investigators, will be tabulated as AEs or SAEs and will appear in individual AE listings.

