## 8.3. Vital Signs

Listings of vital sign results will not be presented. Significant vital sign values, as assessed by the Investigators, will be tabulated as AEs or SAEs and will appear in individual AE listings.

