## 8.4. Physical Examination

Listings of individual physical examinations results will not be presented. Significant results, as assessed by the Investigators, will be tabulated as AEs or SAEs and will appear in individual AE listings.

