## 8.5. Electrocardiograms (ECG)

Listings of individual ECG parameters (including HR, PR, QRS, QT and QTCF) will not be presented. Significant results, as assessed by the Investigators, will be tabulated as AEs or SAEs and will appear in individual AE listings.

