## 9. TABLES AND LISTINGS

## Table 1: Data Summary Tables and Listings

Table Number	Table Title	Population		
14.1	Demographic Data			
14.1.1	Disposition			
	Summary of Subject Dispositions	Safety Analysis Population		
14.1.2	Demographics			
	Summary of Demographics and Baseline Characteristics	Safety Analysis Population		
14.3	Safety Data			
14.3.1	Displays of Adverse Events			
14.3.1.1	Summary of Treatment Emergent Adverse Event	Safety Analysis Population		
14.3.1.2	Summary of Treatment Emergent Adverse Event by System Organ Class and Preferred Term	Safety Analysis Population		
14.3.1.3	Summary of Treatment Emergent Adverse Event by Preferred Term	Safety Analysis Population		
14.3.1.4	Summary of Treatment Emergent Adverse Event by System Organ Class, Preferred Term and Maximum Severity	Safety Analysis Population		
14.3.1.5	Summary of Treatment Emergent Adverse Event by System Organ Class, Preferred Term and Relationship to Study Drug	Safety Analysis Population		
14.3.1.6	Summary of Treatment Emergent Serious Adverse Event by System Organ Class, Preferred Term	Safety Analysis Population		

14.3.1.7	Summary of Treatment Emergent Serious Adverse Event led to discontinuation of study by System Organ Class, Preferred Term	Safety Analysis Population	
Listing Number	Listing Title	Population	
16.2	Participant Data Listings		
16.2.1	Discontinued Subjects		
	Participant Disposition	Safety Analysis Population	
16.2.4	Demographic Data		
	Demographic and Baseline Characteristics	Safety Analysis Population	
16.2.7	Adverse Event Listing		
16.2.7.1	Listing of All TEAEs	Safety Analysis Population	
16.2.7.2	Listing of All TESAEs	Safety Analysis Population	
16.2.7.3	Listing of All TEAEs Leading to Study Discontinuation	Safety Analysis Population	
16.2.7.4	Listing of All TEAEs Leading to Deaths	Safety Analysis Population

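### The SAP drops the lab and vital-sign summaries planned in Protocol 10.2, and none of its 15 outputs calls for an on-treatment value or counts subjects meeting the Protocol 7.1 liver or weight/BMI limits

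*SAP*

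**What the plan says.** Protocol 3 and SAP 3.1 give long-term safety as the aim, with no efficacy objective. Protocol 10.2 plans to summarise vital signs and laboratory results descriptively as change from screening. It does not mention ECG.

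SAP 3.1 states: "Descriptive summary of vital signs, clinical laboratory parameters, and ECG results during the treatment period will not be performed, as identified in the protocol". The listings go as well:

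- SAP 8.2: "Listings of individual laboratory parameters by visit will not be presented".
- SAP 8.3: "Listings of vital sign results will not be presented".
- SAP 8.4: "Listings of individual physical examinations results will not be presented".
- SAP 8.5 likewise withholds "Listings of individual ECG parameters".

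The replacement route, in the words of SAP 8.2, is: "Significant laboratory results, as assessed by the Investigators, will be tabulated as AEs or SAEs and will appear in individual AE listings". Sections 8.3 to 8.5 repeat it for their own assessments, and SAP 4.1 applies it to the C-SSRS. The route agrees with Protocol 9.1, which counts as adverse events "new clinically significant abnormalities in clinical laboratory, physiological testing, or physical examination".

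A second, indirect route exists. SAP 7.1 tabulates the reasons for stopping treatment and lists the reasons for premature withdrawal.

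SAP 2.1 explains that the plan is abbreviated because the study and the program are closing. No full study report is expected, and the safety data are meant for the 2025 DSUR. Against SAP 8.2 to 8.5, SAP 6.3.2 and 6.4.1 each say, without exception, that all data will be listed.

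**The concern.** The protocol sets numeric limits for ALT, AST, ALP, bilirubin and weight/BMI and schedules the measurements regularly. The planned outputs contain none of the resulting values. With no full study report expected, those outputs are in effect the planned account of the study.

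Liver is where the loss matters most. Protocol 2.2 describes a 6-month rat study with liver injury and raised ALP and bilirubin. At its NOAEL the AUC margin over the study dose was 1.6-fold. The protocol leaves open whether the effect is confined to rats. A single-arm extension cannot attribute enzyme elevations to the drug, but it can report how many subjects crossed the protocol's own limits. Adverse event terms cannot give that number.

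**Working it through.** No stated figure needs reproducing. The check is a count of outputs, a count of criteria, and a trace of where a subject who meets a limit would appear.

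**1. Outputs in SAP Section 9**

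- Tables: 14.1.1, 14.1.2, and 14.3.1.1 to 14.3.1.7, so 2 + 7 = 9.
- Listings: 16.2.1, 16.2.4, and 16.2.7.1 to 16.2.7.4, so 2 + 4 = 6.
- Total: 9 + 6 = 15.
- Adverse event outputs: 7 + 4 = 11. The other 4 are two on disposition and two on demographics and baseline.
- Outputs calling for an on-treatment lab or vital-sign value: 0. Outputs counting a Protocol 7.1 limit: 0.

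**2. Criteria in Protocol 7.1**

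| Criterion | What a count needs |
|---|---|
| ALT/AST at least 4 × ULN | Lab values only |
| ALT/AST at least 3 × ULN with bilirubin at least 2 × ULN | Lab values only |
| ALT/AST at least 3 × ULN with symptoms | Lab values plus AE data |
| ALP above 3 × ULN | Lab values, before attribution |
| ALP above 2.5 × ULN with bilirubin above 2 × ULN | Lab values, before attribution |
| ALP above 2.5 × ULN with symptoms | Lab values plus AE data, before attribution |
| Weight loss of at least 2 kg giving BMI below 18.5 | Weight, height and a reference visit |

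That is 6 + 1 = 7 criteria with a numeric part. The condition that an ALP rise be of hepatic origin and drug-related governs all three ALP rows. Two further criteria come from the C-SSRS. They rest on endorsed items or reported behaviour and have no numeric limit, so they fall outside the count.

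**3. Where a subject meeting a liver limit would appear**

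For liver tests, Protocol 7.1 asks only that discontinuation be considered, in consultation with the medical monitor. Four cases follow:

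- AE entered, treatment stopped: TEAE outputs, "Listing of All TEAEs Leading to Study Discontinuation", and disposition. The only *table* of events leading to discontinuation, 14.3.1.7, is restricted to serious events.
- AE entered, treatment continued: TEAE outputs.
- No AE, treatment stopped: possibly a disposition reason.
- No AE, treatment continued: nowhere.

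In the first two cases the output need not show the ULN multiple or the paired bilirubin. SAP 6.3.4 reports events by preferred term and body system, and Protocol 9.2 grades severity on functioning. Nor does Protocol 9.1 set a numeric floor for an adverse event, so an enzyme AE may be entered below every limit. A count of AE terms therefore bounds the number of crossings neither from above nor from below.

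**4. What a count could say (illustration only)**

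The documents give a cap of 180 subjects but not the number dosed, so n is an assumption. If no subject crossed a limit, the exact one-sided 95% upper bound is 1 − 0.05^(1/n):

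- n = 180: 1.65%.
- n = 100: 2.95%.

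The chance of at least one crosser among 180 is 1 − (1 − p)^180. It is 59%, 84% and 97% for assumed rates p of 0.5%, 1% and 2%. The present outputs support no such statement.

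**The case against.** The strongest reply is that the change is deliberate and disclosed. SAP 2.1 gives program closure as the reason, SAP 2.3 says the analyses were modified, SAP 3.1 names what is dropped, and SAP 8.2 to 8.5 state the substitute route. That stands, and nothing here suggests concealment. Closure explains the cut, but it does not supply the values.

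A reader might infer that the SAP removed a planned count of stopping-limit crossings. The documents do not support this. Protocol 10.2 planned change summaries, which need not have counted crossers. They were also loosely defined, since neither schedule of events has a screening visit.

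A reader might also infer that adverse events are the only route. Disposition reasons are a second one. They matter most for the C-SSRS criteria, where Protocol 7.1 says study drug should be discontinued, and for weight/BMI, which it calls a stopping criterion.

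The missed-subject case needs a result at a stopping limit to be judged not significant and no AE to be entered, despite the expected consultation. It is possible, but the documents do not say how likely. The AE listing columns are also unspecified, so a value might happen to be shown. Finally, SAP 6.3.2 and 6.4.1 promise that all data are listed. The specific text of SAP 8.2 to 8.5 and the Section 9 list point the other way, and the zero in step 1 follows them.

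**Conclusion.** The point holds and should be fixed. The SAP withdraws the lab and vital-sign summaries of Protocol 10.2 and the related listings. None of its 15 outputs calls for an on-treatment lab or vital-sign value, and none of the seven Protocol 7.1 criteria with a numeric part is counted. The number of subjects who crossed a limit without appearing in any output cannot be derived.

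Two stronger conclusions do not follow. Liver safety did not go unmonitored: Protocol 4 provides for ongoing review by an independent DSMB. The data are not lost either: SAP 6.3.6 maps them to SDTM, and SAP 2.2 permits further analyses, though it does not expect post-hoc ones. The gap is in the planned outputs alone.

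The closing clause of the SAP 3.1 sentence is ambiguous. Read as saying that the protocol leaves these summaries out, it would be wrong for labs and vital signs.

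The conclusion assumes that SAP 8.2 to 8.5 and Section 9 prevail over the general all-data sentences.

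**What to change.** 1. Add one table to SAP Section 9: number and percentage of Safety-population subjects with any on-treatment value meeting the numeric part of each of the six liver criteria and the weight/BMI criterion, as Protocol 7.1 writes them. Label the counts as threshold crossings. Show all three ALP criteria before Investigator attribution. Flag the two symptom-linked criteria (one ALT/AST, one ALP) by cross-reference to AE data. Protocol 7.1 names no reference visit for weight loss, so state one as an analysis convention only.
2. Add one listing of those subjects with values, visit, any linked AE and disposition.
3. Reconcile the all-data sentences in SAP 6.3.2 and 6.4.1 with SAP 8.2 to 8.5 and Section 9, and say whether weight and C-SSRS data are listed. Reword the closing clause of the SAP 3.1 sentence to make clear that Protocol 10.2 does plan the lab and vital-sign summaries.

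The cost is SAP wording, one table and one listing, from data already collected and due to be mapped to SDTM. The downside is modest extra programming in an abbreviated close-out deliverable, including a merge with AE data for the symptom-linked criteria. It assumes that reference ranges are held with the lab results, which the documents do not state.
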